- **Fidelity Protocol:** The fidelity of the text-message component is assured, as all text-messages will be automated. To assess fidelity of in-person ED sessions, all will be audio-taped. The interventionist's first 10 tapes will be rated by Drs. [name] and [name], *according to guidelines to be developed in Aim 2*, to objectively evaluate if there is protocol drift. If tapes meet the 80% criterion, 20% of recordings thereafter will be coded. Criteria for adherence to the ED session will be defined in terms of specific content areas, as well as adherence to basic CBT and MI principles.[49-51] **This will serve as a training activity.**

- **Incentives:** Maximum compensation for completion of the entire trial will be \$150 (\$25 for baseline, \$40 for 8-week follow-up, \$50 for 16-week follow-up, \$20 for unlimited text-messaging plan for 8 weeks, \$5 for alerting us to a change in phone number, \$5 each for finishing the 8 & 16 week follow-ups online). [name] and [name] have successfully recruited and retained 80-90% of participants for 12-month follow up across multiple trials with high-risk adolescent ED patients, using similar protocols and compensation.[42, 47, 89]

Mental Health Safeguards and Data Management: The research assistants will be extensively trained by the PI and Mentor [name] to recognize and manage participant distress. In case of severe depressive symptoms, suicidality, or other crises during in-ED screening, the interventionist will immediately notify the PI and the attending emergency physician. If mental health crises are identified during interviews outside the ED, the research team will contact the PI at time of identification and refer appropriately, according to the drafted crisis plan. Mentor [name], a licensed clinical psychologist, will be available by phone for clinical decision-making. Please see **Human Subjects** for further details.

STATISTICAL ANALYSIS

PHASE ONE, Aim 2: Using data collected during the open trials, we will perform a preliminary process analysis, examining study recruitment and refusal rates, study completion rates, use of text messages, follow-up rates, reliability and range of responses to assessments, and overall study attrition. We will study exit interview transcripts for acceptability, treatment satisfaction, and comprehensibility. Exit interviews will also undergo thematic analysis, similar in methodology to Aim 1. Because the interview topics are restricted to review of the revised materials and feedback on planned intervention components, it is likely that most codes will be deductive. Analysis will also focus on key domains that are also covered by the quantitative evaluation instruments so that the qualitative data can provide additional context for that quantitative data.

In addition, as described in Aim 2: Assessments, above, we will assess the text-messages' usability and acceptability by calculating the mean score for the System Usability Scale (SUS)[124, 125] and the Relative Subjective Count (RSC). [127, 128] The SUS will be administered at the close of the 8-week intervention; a higher score correlates with higher usability. The RSC will be calculated based on information obtained in the exit interviews, as successfully used by [name]; lower scores correspond to higher acceptability.[127, 128] We will also review the number and type of ED visits and hospital admissions for the duration of the study to examine trends in hospital admission as an effect of study participation.

Based on these formative data, we will further refine our intervention and study protocol.

PHASE TWO, Aim 3:

- Sample size: For this intervention pilot study, we chose to recruit 120 subjects in the RCT. Conservatively estimating that 20% may be lost to follow-up, 96 subjects will complete the 16-week assessment. This number will be sufficient to allow us to make judgments regarding feasibility and acceptability. Despite problems in the stability of effect size calculations with small samples, if a small effect size is detected between groups, and the intervention is shown to be feasible and acceptable, then further testing in a larger trial may be indicated given the innovative nature of the intervention and its potential disseminability.[138, 139] Based on our Aim 1 results, we anticipate that the mean PHQ-9 score of our participants will be 10.0, with a standard deviation of 4.5. If we wish to show a delta-PHQ9 of 2 (with alpha 0.05 and beta 0.8), we would need to successfully follow up 63 participants.

- Data management: Data from text messaging, including time of delivery and any participant responses, will be stored in a de-identified database on a HIPAA-compliant server. This de-identified data will be imported into Stata 12 (Stata Corp, College Park, TX), with which I and my mentors are skilled. Stata 12 is suitable for the multi-level modeling necessary for a fully-powered longitudinal study.

- Acceptability and feasibility (Aim 3a): *Acceptability* will be measured using descriptive analysis of enrollment rates, participants' ratings of the clarity and structure of the in-person and text-message sessions, Client Satisfaction Questionnaire-8,[48] *Feasibility* will be measured using percent of in-person sessions completed, the RSC (as described in Aim 2).[127, 128] and therapist adherence ratings.

- Exploratory hypothesis testing: We will calculate total scores for depressive symptoms (PHQ-9, BDI-II) and violence exposures (CTS-2, CADRI) at baseline and follow-up. We will calculate descriptive statistics for study sample demographics, baseline mediators/moderators (e.g. IPAS, hopelessness), co-morbidities (CPSS) and service utilization (CASA). T-test and chi-square comparisons will be used to detect baseline between-group differences.

The *primary exploratory outcome* of interest is depressive symptoms (measured by BDI-II); the *secondary outcome* is peer violence (CTS-2). Under [name] guidance, we will first calculate preliminary estimates of the between-groups differences in depressive symptoms (continuous) and peer violence (counts), with 95% confidence intervals, at 8- and 16-week follow-up assessments, adjusted for baseline values. An intent-to-treat approach (all patients randomized to intervention will be retained in analysis) will be used to address potential problems inherent in following only treatment completers and the potential for differential attrition across conditions.[140, 141] In cases of loss-to-follow-up, baseline observations will be carried forward.

Generalized linear mixed models (GLMM)[142, 143] that employ likelihood-based estimation approaches will then be used to evaluate changes in depressive symptoms and number of fight episodes at the 8-week and 16-week follow-ups. Intervention condition will be considered the primary predictor variable. Race and gender will be included as secondary predictors. We will control for baseline levels of the outcome variable (e.g. severity of baseline depressive symptoms and peer violence) as well as the linear and quadratic effects of time. We will also examine potential moderators of the intervention effect, including gender, race, and baseline coping skills. In GLMM, no missing data imputation will be employed, as the models produce consistent estimates in the presence of data missing-at-random.[144, 145] **Analyses will serve as a training activity.**

Potential Problems & Alternative Strategies: Parental involvement: According to pilot data, 99% of eligible adolescents seen in our ED are accompanied by a parent. We recognize the importance of parents in teens' mental health, but we have chosen not to include parents any further than the consent process, in order to focus on acceptability for adolescents,[146] and to increase feasibility and eventual disseminability. Difficulty completing in-person session during time in ED: My mentorship team has successfully completed multiple studies with 45-60 minute CBT- and MI-based interventions for teens in the ED. Enrollment biases: Patients who are more symptomatic or more comfortable with technology may be more likely to enroll. In our planned R01 we will correct for these characteristics by stratifying by baseline symptom severity, and by including technology use as a covariate; we will also adapt the intervention for Spanish speakers. Attrition of participants: Our study recruitment location has a strong track record in retaining our target population in long-term studies. I will conduct weekly meetings with staff to identify potential threats to participant retention. The native attraction of text-messaging to adolescents should help prevent fatigue from intervention use.[39, 147, 148] Although we anticipate 15-20% attrition based on past work, we believe that we can respond rapidly and effectively to any potential difficulties. Technology difficulties: Through the PI's foundation grant and [name] NIMH-funded R34, we have successfully piloted the text-message technology that we propose to use in this project. Cell phone concerns: Participants will be compensated for their monthly text-messaging plans. See **Human Subjects** for details on protection of confidential information, and for mechanism to regain contact in case of changed phone numbers.

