- **“Text” component (daily for 8 weeks):** Based on results from Aim 1, we will sending *one automated assessment followed by one tailored CBT-informed text message each day*, at a time of the participant’s choice. Each week, a variety of messages will be delivered to create both (a) a natural progression in skill-building; (b) continued motivation for participation; and (c) responsiveness to participants’ needs, through tailoring. This daily text-message system will maximize active engagement and increase participants’ practice of key CBT-based concepts, which has been shown to correlate with change in depressive symptoms.[84] We will also provide *participant-driven text-messages*: e.g., if the participant texts “FIGHT” or “MOOD” to the automated program, indicating need for additional support on that topic, s/he would receive an appropriate skill-based message.

After each round of open testing, message prompts, content, and frequency will be **iteratively refined based on qualitative and quantitative assessments**. Final content will be submitted to the IRB prior to the start of Aim 3 (at which point the intervention will not be further revised). The current conception of the messages and the delivery algorithm are attached as **Appendix 3** (“TEXT MESSAGES”).

Messages will be delivered to participants’ own cell phones using an automated computerized system developed by an outside company, Reify Health, based on pre-specified delivery algorithms. Any responses that deviate from expected requests will receive an automated “crisis message.” Data from the responses will be reviewed weekly, and will be visible ONLY to members of the research team (see **Human Subjects**). (see **Appendix 3** and **Human Subjects** below).

PI [name] used this system to conduct daily mood assessments of high-risk adolescent girls in a pilot grant funded by a private foundation with over 80% response rates to 9 daily messages and overwhelmingly positive feedback during a post-assessment interview. Mentor [name] is currently using Reify Health to deliver text-messages for an NIMH-funded R34 for adolescent suicide prevention. Advisor [name] has successfully delivered interventions to participants using a similar system.

- **Assessments:** In addition to the assessments in the screening protocol, we will administer assessments at the close of the open intervention to guide refinement of the “ED+text” intervention. Specifically, we will

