collect data on feasibility: study recruitment and refusal rates, program completion, follow-up rates, reliability and range of responses to baseline and follow-up questionnaires, and rates of study attrition (see **CODEBOOK AIM 2**). Participants will also complete detailed qualitative debriefing after the in-person and text-messaging components of the intervention (see **QUALITATIVE ASSESSMENT**). This evaluation necessarily occurs on a clinical, non-statistical level. Participant acceptance of the text-messaging will also be assessed by: (1) The *System Usability Scale*, a participant-completed, reliable and valid metric for measuring usability and acceptability of technologies.[123, 124] Higher scores equate to higher usability.[125, 126] (2) *Relative Subjective Count (RSC)*, the quotient of the participant’s estimate of the number of times the system delivers a text, divided by the actual number of texts delivered.[127, 128] As text-message systems are unable to track actual number of texts opened, this measure is a reliable surrogate measure of acceptability.[127, 128] Low RSC (e.g., <1.0) correlates with increased participant satisfaction, while elevated RSC (>1.0) reflects poor acceptability of a technology (e.g. that the messages were intrusive).[127, 128] Lastly, in recognition of the NIH’s move toward “learning healthcare system” outcomes, we will include a review of Lifespan electronic medical records (EMR) to determine participants’ ED visits and admissions over the 8 weeks of the study period, to show the feasibility of tracking this data. We will extract only the number, category, and disposition of the visits (specifically, whether the visit was related to injury, psychiatric complaints, or medical complaints, and whether the patient was discharged, transferred [as well as transfer location], or admitted to Hasbro) from the Lifespan EMR.

Aim 3: Conduct a pilot randomized trial of the novel “ED+text” intervention versus enhanced usual care (EUC).

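### The Relative Subjective Count is a ratio read against 1.0 but summarised by its mean, which a few large over-estimates can lift above 1.0 when most participants are below it (minor)

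*Combined protocol and SAP*

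**What the plan says.** The Assessments paragraph under Aim 2 defines the RSC as the participant's estimate of the number of texts, "divided by the actual number of texts delivered". It then gives the reading: "Low RSC (e.g., <1.0) correlates with increased participant satisfaction, while elevated RSC (>1.0) reflects poor acceptability of a technology".

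The Statistical Analysis section, Phase One (Aim 2), assesses usability and acceptability by "calculating the mean score for the System Usability Scale (SUS)[124, 125] and the Relative Subjective Count (RSC"). It adds that "The RSC will be calculated based on information obtained in the exit interviews" and that "lower scores correspond to higher acceptability".

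In Phase Two, the Aim 3a paragraph says that feasibility "will be measured using percent of in-person sessions completed, the RSC (as described in Aim 2"), with therapist adherence ratings as the third measure. Table 11.3 places the RSC at the 8-week assessment.

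No section names a median, a geometric mean, a log scale, an outlier rule or the share of participants above 1.0 for the RSC. Aim 3a in the Specific Aims sets numerical criteria for enrolment, satisfaction ratings, session completion and session adherence. It sets none for the RSC.

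**The concern.** The numerator is a recalled count of eight weeks of daily texts, so some guesses may be far too high. A guess can fall short by at most the whole delivered count (RSC of 0), but it can exceed that count by any amount. One high guess can therefore offset several moderately low ones in a mean. The plan's own question is on which side of 1.0 participants fall, and a mean does not answer it when the distribution has a long right tail.

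What is at stake is how a process measure is read. The RSC is one of three measures listed for Aim 3a feasibility, and feasibility is among the primary outcomes of Aim 3. In Aim 2 it is among the results available when the texts are revised. A mean just above 1.0 could suggest that the messages are intrusive when most participants' ratios point the other way.

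**Working it through.** The plan states no expected RSC, spread or pass mark, so there is no figure to reproduce. From the documents come the definition of the ratio, the reference value 1.0, the Aim 2 sample (16 to 20) and the 96 participants expected to complete Aim 3 at 16 weeks, used here as a guide to its size. All RSC values below are assumptions.

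**Step 1: how few high values are enough.** If k of n participants have ratio H and the rest have ratio L, the mean is [(n − k)L + kH]/n. It exceeds 1.0 when k > n(1 − L)/(H − L).

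- n = 16, L = 0.9, H = 3.0: 16 × 0.1/2.1 = 0.76, so k = 1. Mean = (15 × 0.9 + 3.0)/16 = 16.5/16 = 1.03; median 0.90; 15/16 = 94% below 1.0.
- n = 16, L = 0.8, H = 3.0: 16 × 0.2/2.2 = 1.45, so k = 2. Mean = (14 × 0.8 + 6.0)/16 = 17.2/16 = 1.075; median 0.80; 14/16 = 87.5% below 1.0.
- n = 16, L = 0.7, H = 2.0: 16 × 0.3/1.3 = 3.69, so k = 4. Mean = (12 × 0.7 + 8.0)/16 = 16.4/16 = 1.025; median 0.70; 12/16 = 75% below 1.0.
- n = 96, L = 0.8, H = 3.0: 96 × 0.2/2.2 = 8.7, so k = 9. Mean = (87 × 0.8 + 27)/96 = 96.6/96 = 1.006; median 0.80; 87/96 = 91% below 1.0.

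**Step 2: how much spread is needed.** For a log-normal ratio with median m and log-SD s, the mean is m × exp(s²/2). It exceeds 1.0 when s > √(−2 ln m).

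- m = 0.9: √0.211 = 0.46
- m = 0.8: √0.446 = 0.67
- m = 0.7: √0.713 = 0.84

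With m = 0.8 the population mean is 0.84, 0.91 and 1.02 at s = 0.3, 0.5 and 0.7.

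**Step 3: what that spread means in texts.** One assessment and one message a day for 8 weeks is 2 × 56 = 112 texts, so a median ratio of 0.8 is a guess of about 90. The central 95% of guesses is 89.6 × exp(±1.96s). At s = 0.3 the factor is 1.80, giving about 50 to 161. At s = 0.67 it is about 3.7, giving about 24 to 332.

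**Step 4: how often mean and median disagree.** In 100,000 simulated log-normal samples with true median 0.8, the chance that the sample mean is above 1.0 while the sample median is below 1.0 was:

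| log-SD | n = 16 | n = 96 |
|---|---|---|
| 0.3 | 0.6% | about 0% |
| 0.5 | 15% | 3% |
| 0.7 | 36% | 59% |

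**The case against.** The strongest reply is that nothing in the plan turns on the RSC. The Aim 3a criteria do not use it, the value below 1.0 is offered only as an example, and it is tied to satisfaction as a correlation. A reader might infer that a mean above 1.0 would make the programme fail on feasibility. The documents contain no such rule, and this part of the reply stands in full.

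A reader might also infer that the mean is wrong in principle because 0.5 and 2.0 average 1.25. That treats halving and doubling as equal errors, which the documents do not say. If estimates are right on average as counts, the expected ratio is exactly 1.0. The narrower point survives: the mean is sensitive to a few high values and does not show where most participants lie.

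A third tempting reading is that a larger sample never helps. At a given spread the ratio of population mean to median is fixed, but the chance of crossing 1.0 falls with n whenever the population mean is below 1.0, as the 0.5 row of the table shows. It rises with n only when the population mean is itself above 1.0.

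Finally, a reader might suppose that each Aim 2 round of four is judged by its own mean. The plan does begin "After each round of open testing, message prompts, content, and frequency will be" iteratively refined on qualitative and quantitative findings. However, the statistical section describes the mean for the open trials as a whole, and the Assessments paragraph calls the evaluation clinical rather than statistical. The plan also reviews the range of responses, the System Usability Scale and the exit interviews, so the RSC would not be read alone.

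The wording also allows another parse, in which the mean belongs to the usability scale alone. The RSC would then have no stated summary, and the same edit would supply one. The Aim 3a paragraph refers back to Aim 2 without repeating the word mean.

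**Conclusion.** The point holds as a minor one. On the ordinary reading, the plan summarises by its mean a ratio that it interprets against 1.0, and names no companion figure that would show a long right tail. One participant in 16 can be enough to move the mean across the line if the rest sit just below it.

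How likely this is cannot be settled from the documents, because they give no spread. Under the log-normal assumption with median 0.8, it hardly occurs at a log-SD of about 0.3 and becomes common above about 0.67. The consequence is limited to the interpretation of a descriptive acceptability and feasibility measure. Sample size, error rates and the stated success criteria are untouched.

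**What to change.** In the Statistical Analysis section, Phase One (Aim 2), state that the RSC will be reported as the median with interquartile range, together with the percentage of participants whose RSC is above 1.0, and that these figures are the ones read against 1.0. The Aim 3a paragraph inherits this through its reference to Aim 2; repeating it there would remove doubt. The mean RSC may be kept as a secondary figure, and the mean remains suitable for the System Usability Scale.

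The cost is one sentence, with no new data and no extra participants. The downside is that the median is slightly less efficient than the mean if the guesses prove nearly symmetric.

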In this K23 research plan, we will create an indicated depression prevention intervention for teens seen in the ED with depressive symptoms and a history of peer violence. Drawing on effective CBT and motivational interviewing (MI) depression and violence prevention interventions,[42-45] a brief in-person session ("ED") will introduce basic cognitive and behavioral strategies. Following ED discharge, eight weeks of tailored CBT-informed daily text messages ("text") will be sent, to enhance skills and remind participants of self-determined goals. The "ED+text" intervention may be more accessible and disseminable for this high-risk population.[46]

My long-term goal is to become an expert in easily-disseminated, technology-assisted mental health interventions for high-risk ED patients. Although such interventions may have a modest effect, I am purposely designing them to have a broad reach for the large group of ED patients who do not access any mental health care. My short-term goals, for this K23 award, are to gain training in development and analysis of technology-assisted ED depression prevention interventions, and to test the hypothesis that an "ED+text" indicated depression prevention intervention is acceptable and feasible. This study will lead to an R01 application to conduct formal efficacy testing.

We are currently completing our recruitment for, and analysis of, Aim1 (qualitative interviews to develop the intervention). THIS APPLICATION IS FOR APPROVAL OF AIMS 2 and 3.

Aim 2: Refine intervention content. Eligible participants will be iteratively enrolled, 4 at a time, in the "ED+text" intervention (n=16-20). Through semi-structured interviews and measures of protocol adherence, we will refine content and improve feasibility, acceptability, usability, and clarity of the intervention components.

Aim 3: Conduct a randomized pilot trial (n=120) of the "ED+text" preventive intervention vs. enhanced usual care (attention-matched nutritional text messages).

3a: Primary outcomes will be intervention acceptability (defined as 65% enrollment rates and 80% agree/strongly agree ratings[42, 47] on the Client Satisfaction Questionnaire-8[48] and exit interviews), feasibility (defined as 80% completion of in-person and text-message sessions[42, 47]) and fidelity of in-person sessions (defined as 80% adherence to session manual[49-51]).

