3b: Preliminary hypothesis testing: Although not powered to detect efficacy, we will look for a trend toward a primary outcome (a decrease in depressive symptoms at 8 and 16 weeks), and an exploratory secondary outcome (decreased number of peer fights) relative to enhanced usual care.

This proposal is innovative: it will develop a feasible, acceptable depression prevention intervention for a high-risk population of adolescent ED patients with a history of peer violence. It also has high significance and impact: utilizing the ED location, it addresses a current lack of easily-accessible preventive services and reflects NIMH Strategic Objectives 3 and 4. It will potentially lead to an efficient means to reduce depressed mood in high-risk teens with little access to traditional mental health care. If effective, this intervention will be

translated to other at-risk patients seen in the ED. Finally, it is essential for my career development as an ED-based mental health intervention researcher.

RESEARCH STRATEGY

(a) SIGNIFICANCE: Prevention of adolescent mental health disorders and peer violence are critical research goals according to Healthy People 2020, NIMH, and the Institute of Medicine.[52-55] Mood disorders are epidemic among teens,[6-8, 56] and strongly correlate with a history of physical peer violence (assault or victimization).[5, 14, 15, 57-59] Rates of youth violence are also high,[60, 61] many causing severe injury: over 650,000 youth presented to the ED for violent injuries in 2008 alone.[62] In a national study of 4023 adolescents, 39% of teens with a history of assault (vs. 5% of teens with no trauma history) met criteria for major depressive disorder (MDD).[3] My pilot work shows that 40-60% of adolescents with a history of physical peer violence report past-month depressive symptoms, as compared to 17-20% of all teens seen in the ED.[9, 63-65] These rates are substantially higher than the 5-10% average 30-day prevalence of depressive symptoms in community samples of teens.[7, 66] Just as EDs screen for high-risk alcohol use or partner violence, a positive screen for past-year peer violence is a marker of being high risk for both MDD and future violent injury.[25, 67-72]

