14. PROTECTION OF HUMAN SUBJECTS

Summary: For this clinical study, all data collection sheets and computerized databases will use a unique numeric code to identify specific subjects. The code sheet will be kept in a locked file cabinet in [name] locked office, and on password protected files on secure hard drives owned by [name] institution. We intend to seek approval for this study from the human protection committees at Rhode Island Hospital; no study activities will be initiated without full institutional review board approval. All members of the research team have already completed training and received certification in Human Subjects Research Protection (CITI Program) and HIPAA regulations. They will continue to renew this training in compliance with Rhode Island Hospital and Brown University policies. Additionally, **a Certificate of Confidentiality will be obtained** for this study from NIH once IRB approval has been granted.

14a. Risks to the Subjects

14a.1. *Human Subjects Involvement and Characteristics:*

In Specific Aim 2, approximately 16 adolescents will participate in a series of open trials of the ED-based preventive intervention. In Specific Aim 3, the novel "ED+text" intervention will be studied in a randomized controlled pilot trial, with 50 participants in the "ED+text" arm and 50 participants in the enhanced usual care (EUC) arm. The ethnic and racial composition of the study group will be expected to represent that of the pediatric population seen in the Rhode Island Hospital ED, identified to be approximately 40% Hispanic and 25% black or African American by my own pilot study (data analysis in progress). Children aged 13 to 17 will be included in the study.

Inclusion Criteria. To recap what was described in Section 11c above: *Inclusion criteria for screening include:* being medically stable; mentally and physically able to assent; English-speaking; and having a parent present to consent. *Exclusion criteria for screening include* a chief complaint of sexual assault or child abuse; a chief complaint of acute suicidality or psychosis; or being in police custody. *Additional inclusion criteria for enrollment (in Aim 2 or Aim 3) include* a PHQ-9 score ≥ 5 and past-year peer violence (according to CTS2).

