[name] will ensure that all relevant IRB policies, procedures and stipulations are being followed. [name] also will be responsible for ensuring that other investigators and project staff adhere to the RIH IRB policies including the following: (1) All participants in the full Aim 2 and Aim 3 studies will understand, agree to, and sign a written assent form (and consent from parent/guardian) before participating; (2) Strict adherence to a participant's right to withdraw or refuse to answer questions will be maintained; (3) All interviews and assessments will be completely confidential and no names will be associated with the data; (4) Consent forms and identifying information will be kept separate from the actual participant data; (5) All identifying information (consents, tracking data) will be kept locked at all times and computer files will be saved with passwords; and (6) Participants will be informed in writing in the consent form on how to contact the PI, the study coordinator, and IRB office with any questions and/or concerns.

Weekly meetings with [name] will be conducted to evaluate the progress of the trial and to review data quality, recruitment, study retention, and examine other factors that may affect outcome. Participant experiences and the rates of adverse events will also be reviewed to determine any changes in participant risk. [name] will report any adverse events that are observed to the IRB within one week of occurrence, and to NIMH in our annual report. Serious adverse events (SAEs) will be reported to the IRB within 2 work days of our receipt of information regarding the event; if deemed to require a change in protocol, NIMH will also be notified. Reports of changes or amendments to the protocol in general must be requested first in writing to the IRB, which then will grant or deny permission to make the requested change or amendment in protocol.

Finally, if significant homicidal, suicidal, or mental health risks occur during the study period, the participant's parent(s) will be notified, as described in **14b.2. Protection against risks** (above), and evaluation by the Rhode Island Hospital crisis team will be immediately initiated to determine whether hospitalization is needed.

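### The Aim 3 randomised trial has two sizes, 120 and 50 + 50 = 100, and the stated 96 completers follow only from 120

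*Combined protocol and SAP*

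**What the plan says.** Two places give a total of 120:

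- Specific Aims, Aim 3: "Conduct a randomized pilot trial (n=120".
- Statistical Analysis, Phase Two, Aim 3, Sample size: "we chose to recruit 120 subjects in the RCT". Allowing for 20% loss, the same paragraph concludes that "96 subjects will complete the 16-week assessment" and treats that number as enough to judge feasibility and acceptability.

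Two places give 50 per arm:

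- Aim 3, Study Randomization and Intervention Conditions: eligible participants are randomised to ED+text (n=50) or enhanced usual care (n=50).
- Section 14a.1, Human Subjects Involvement and Characteristics: 50 in the ED+text arm and "50 participants in the enhanced usual care (EUC) arm".

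Three other statements bear on the point. Potential Problems & Alternative Strategies says "we anticipate 15-20% attrition based on past work". The Specific Aims say "THIS APPLICATION IS FOR APPROVAL OF AIMS 2 and 3". Aim 3b says of the efficacy comparison: "Although not powered to detect efficacy".

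**The concern.** The same trial is given two randomised totals, each stated twice, in one document submitted for approval. The documents contain no amendment log that would mark either figure as superseded.

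The number of minors to be randomised is a basic term of ethics approval. The human-subjects section tells the IRB 100, while the aims and the statistical section say 120. If approval rested on 100, enrolling participants 101 to 120 would raise a compliance question. If it rested on 120, stopping at 100 would fall short of the plan. The text alone does not tell staff which number closes enrolment, or how many 16-week completers to expect.

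**Working it through.** **Inputs**

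| Quantity | Value | Source |
|---|---|---|
| Total randomised, A | 120 | Specific Aims, Aim 3; Sample size |
| Total randomised, B | 50 + 50 = 100 | Study Randomization and Intervention Conditions; 14a.1 |
| Loss to follow-up | 20% | Sample size |
| Loss to follow-up, range | 15-20% | Potential Problems & Alternative Strategies |
| Completers at 16 weeks | 96 | Sample size |
| PHQ-9 SD and difference of interest | 4.5 and 2 points | Sample size |

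**Step 1: reproduce the plan's figure.** Completers = N × (1 − loss). With N = 120 and 20% loss, 120 × 0.80 = 96, exactly as stated.

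**Step 2: apply the same formula to both totals.**

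| Loss | N = 120 | N = 100 | Difference |
|---|---|---|---|
| 20% | 96 | 80 | 16 |
| 15% | 102 | 85 | 17 |

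**Step 3: loss needed to get 96 from 100.** 1 − 96/100 = 4%, well below the range the plan expects.

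**Step 4: consequence for precision.** Interval width scales with 1/√n, and √(96/80) = 1.095, so intervals are about 10% wider with 80 completers than with 96. Two illustrations:

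- *A feasibility or acceptability proportion of 80%*, closest to the primary aims. The 95% half-width is 1.96 × √(0.8 × 0.2/n). This is 8.0 percentage points at n = 96 and 8.8 at n = 80. In one arm as randomised, it is 10.1 points at n = 60 and 11.1 at n = 50.
- *An unadjusted difference in PHQ-9*. The 95% half-width is 1.96 × 4.5 × √(2/n per arm). This is 1.80 points at 48 per arm and 1.97 at 40 per arm. Two-sided t-test power at alpha 0.05 for a 2-point difference is about 58% and 50%. The plan does not state sidedness; one-sided, by normal approximation, power is about 70% and 63%. This is not the planned analysis, which is baseline-adjusted and uses the BDI-II, for which no SD is given.

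**Step 5: does the plan's follow-up number of 63 settle the total?** It does not. Reading the stated target as 80% power, 63 is reproduced as a per-arm number with one-sided alpha 0.05: 2 × (1.645 + 0.842)² × 4.5²/2² = 62.6, rounded up to 63. That means 126 followed up, more than either total would yield. If 63 is read as an overall number, both 96 and 80 exceed it. Neither reading points to one total.

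**The case against.** Several readings could make the figures compatible, but none survives the text.

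- *The 50s are completers.* The randomisation paragraph gives them as numbers randomised, and 100 is not the stated completer count of 96.
- *The 120 includes up to 20 Aim 2 participants.* The Specific Aims count Aim 2 separately (16-20), the sample-size paragraph places all 120 in the RCT, and 14a.1 makes Aim 2 participants ineligible for Aim 3.
- *120 are recruited and 100 randomised.* The Specific Aims attach 120 to the randomised trial itself, and no loss before randomisation is stated.
- *There is a third arm.* Aim 3 specifies a two-group design.

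The stronger objection concerns weight. The calculation 120 × 0.80 is correct, so this is an inconsistency in N and not a computing error. Efficacy is exploratory, no threshold or analysis method changes, and the loss of precision is small. At the plan's conservative estimate of about 20 participants a month, the gap is roughly one month of recruitment. The aims, the sample-size section and the completer count all agree on 120, so the 50s may be leftover text.

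All of that stands, and it limits the statistical consequence. It does not establish which number was approved, and the documents do not say that the 50s are out of date.

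**Conclusion.** The contradiction is real and must be corrected. It amounts to 20 participants randomised and 16 fewer completers at 20% loss (17 at 15%). The 96 completers on which the plan bases its claim of sufficiency cannot be reached from the arms as described at the plan's own attrition.

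The case for correction rests on the enrolment target and the human-subjects count, not on lost power. The internal evidence leans towards 120, but the approved number cannot be inferred from the documents. The completer counts assume that the plan's loss rates apply equally under either total. The per-arm figures also assume equal allocation and equal loss in the two arms. Figure 11.1 could not be seen, but whatever it shows, the four text statements would still disagree.

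**What to change.** Confirm the approved number with the IRB, then state one total in all four places: Specific Aims, Aim 3; Study Randomization and Intervention Conditions; Sample size; and 14a.1. Either:

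- **120:** change the randomisation paragraph and 14a.1 to 60 per arm, and keep 96 completers; or
- **100:** change the Specific Aims and the sample-size paragraph to 100, and replace 96 with 80 completers.

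Check Figure 11.1 against the chosen total. If the stratified allocation list was prepared to a fixed length, check that it covers that total.

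The cost is a wording correction in two places plus the IRB confirmation. If the IRB accepted only 100 and the sponsor wants 120, section 14f applies: "Reports of changes or amendments to the protocol in general must be requested first in writing to the IRB".
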